### **2. Purpose**

The purpose of this pilot study is to build upon baseline data on pregnancy intention and receipt of contraceptive and preconception counseling. 2 of the 4 participating practices will be randomly selected to receive comprehensive One Key Question® training through the nonprofit *Power To Decide*. All trained sites also have access to technical support in implementing OKQ. This training and technical support will act as the intervention and be given to help improve the quality of preconception and contraceptive counseling in Primary care and Obstetrics/Gynecology. All participating practices will then be surveyed again to determine changes in contraception and preconception counseling. Following this second round of surveys, the remaining practices will have the option to receive *Power To Decide*'s One Key Question ® training.

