### **3. Methodology**

#### **Part I: Trainings**

- a. 2 of the 4 participating NorthShore Medical Groups will be selected to receive *Power To Decide* OKQ trainings. These become the *intervention practices* and the remaining 2 become *control practices*. The selection of these sites will be determined based on site availability, willingness to participate, and clinic characteristics.
- b. Trainings will be provided to clinicians and staff from the intervention practices.
- c. Trainers from *Power To Decide* will execute OKQ trainings
- d. Trainings consist of:
  - Up to seven hours of training, in-person certification training (Appendix B)
  - Provider and Patient Materials
  - Five hours of consulting (prior to and following training)
  - Post training webinar
  - Provider OKQ Certification (two years for the price of one)
  - Access to a OKQ Provider Portal (only available to certified providers)

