### **Part II: Survey Collection – Starts at least 4 weeks after OKQ Training**

- a. The research team will work with physicians and practice managers at all participating NorthShore practices to select mutually agreeable days for data collection at each site.
- b. On data collection days, patient surveys will proceed using the same procedures as those used for baseline data (EH 18-015). Specifically:
  1. A research assistant (RA) will approach a patient in the waiting room before her appointment. After verbal recruitment and consent, the RA will determine if she qualifies for the study.
  2. If the patient is eligible, the RA will explain the study and ask that she comes back to the waiting room after her appointment to fill out a post-exam survey. The RA will instruct the participant to place completed survey in an envelope.
  3. The RA will collect the survey and offer a \$10 Walgreens or CVS gift card as a token of appreciation for participating in the study.
- c. After patient data collection is complete, the RA will return to each practice to collect surveys from clinicians and staff (Appendix C) at the intervention practices to assess the experience of implementing OKQ and their perceptions of its utility for patients.
  1. OKQ staff will attend clinic staff meetings at intervention practices to introduce the survey in-person in order to increase buy-in among respondents.
  2. Clinicians and staff will receive the survey through an emailed link as well as in paper form:
    - i. A paper survey with a cover letter (Appendix F) attached will act as our consenting process. This cover letter will also include a link to the online version of the survey if they choose to complete the survey online.
    - ii. All clinician and staff will receive an email that includes a copy of the cover letter and a link to the survey online.
  3. All individuals taking these surveys on paper forms will be asked to leave their completed surveys at their clinic in a secure location for the RA to pick up.

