One Key Question: Pilot Study at NorthShore

Statistical Analysis Plan

Clinicaltrials.gov (NCT03947788)

11/17/2020

Patients were excluded from analysis if they reported experiencing menopause or having a hysterectomy or sterilization. Since OKQ is a practice-level intervention, we used intention-to-treat analysis and calculated each practice's rate for each outcome, regardless of whether patients' individual physician had participated in the OKQ training. In each group of patients (baseline time point in control and intervention practices, and post-intervention time point in control and intervention practices), we calculated the percentage receiving reproductive counseling and the percentage who were extremely or very satisfied.

We used chi square tests to compare rates across the two time points within each practice. We also used multivariable logistic regression with an intervention time point interaction (difference-in-differences) term to assess intervention efficacy independent of differences across sites and time trends unrelated to the intervention, controlling for practice type (ob/gyn vs. primary care), patient age, race/ethnicity, and reason for visit. Results are reported as adjusted odds ratios (aOR) and 95% confidence intervals (CI). All analyses were conducted using SAS 9.4 (SAS Inc., Cary, NC).

We calculated a minimum sample size of 260 was needed to observe a 15% between-group difference in the pre-to-post change in counseling rates with 80% power. The statistical significance level for all tests was <0.05.

This research was registered on clinicaltrials.gov (NCT03947788) and approved by NSUHS Institutional Review Board (IRB). Analysis of de-identified data was exempted by the University of Chicago IRB (The University of Chicago, 19-0149; NSUHS, 18-343).

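### The SAP describes its regression as independent of differences across sites, but arm plus binary practice type removes at most two of the three between-practice degrees of freedom

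*SAP*

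**What the plan says.** The regression paragraph of the SAP describes a logistic model with an intervention-by-time interaction, fitted "to assess intervention efficacy independent of differences across sites and time trends unrelated to the intervention, controlling for practice type (ob/gyn vs. primary care"). The full covariate list is "controlling for practice type (ob/gyn vs. primary care), patient age, race/ethnicity, and reason for visit". Age, race/ethnicity and reason for visit are patient-level. Practice type is the one site-level covariate. No practice indicator, practice random effect or cluster term is listed, and the main effects are not written out.

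The same paragraph shows that practice identity is available in both waves: "We used chi square tests to compare rates across the two time points within each practice".

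Protocol section 2 says "All participating practices will then be surveyed again to determine changes in contraception and preconception counseling". Sections 2, 3 (Part I) and 6 describe four practices, two per arm. On how they are surveyed, Part II has the research team agree dates with the practices, "to select mutually agreeable days for data collection at each site", and states that "patient surveys will proceed using the same procedures as those used for baseline data (EH 18-015"). Section 7 gives an overall ceiling of 234 patients and no number per practice.

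**The concern.** A difference-in-differences term cancels any stable gap between the average intervention patient and the average control patient. It does not by itself cancel gaps between two practices in the same arm. Suppose those practices have different counseling rates and one supplies a larger share of the arm's patients in the second wave. The arm's rate then moves although no practice has changed, and the interaction picks this up unless the covariates explain the gap.

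The interaction odds ratio is the only formal between-arm test that the SAP describes, and the wording tells readers that site differences have been taken out of it. If they are only partly out, the estimate can be pushed up or down by how many patients were surveyed where.

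**Working it through.** **The plan's own figure.** The only computable figure nearby is the sample size: "a minimum sample size of 260 was needed to observe a 15% between-group difference in the pre-to-post change in counseling rates". The baseline rate is not stated. Taking 14% (the national figure in Protocol section 1) against 29%, two-sided 5%, 80% power:

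- n = [1.96√(2 × 0.215 × 0.785) + 0.8416√(0.14 × 0.86 + 0.29 × 0.71)]² / 0.15² = 116.6, so 117 per group (234 in total).
- With continuity correction: 130 per group (260 in total).

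The 14% is my inference, so the match may be coincidence. The point does not depend on it; 260 only sets the scale below (260/4 = 65 per arm per wave), with 117 and 130 as alternatives.

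**Degrees of freedom.** Four practices give 4 − 1 = 3 between-practice degrees of freedom. Arm uses one and binary type adds at most one. Over all 16 ways of assigning two types to four practices, arm plus type spans two of three in 12 assignments, one of three in 4 (type constant within each arm), and never three. Four practice indicators span all three, and the interaction stays estimable (rank 6 on 8 practice-by-wave cells). If the six practices in Protocol section 1 were all analysed, the count would be at most two of five.

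**Size of a mix effect.** The practice rates are assumed. There is no true change in any practice; the control mix stays 50:50; the intervention mix starts at 50:50 and shifts in wave two; patient covariates are not modelled (the bias is smaller if they explain part of the gaps).

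Case (a): intervention practices of the same type at 20% and 50%, both control practices at 35%. A shift to 30:70 gives

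- wave-two rate = 0.3 × 20 + 0.7 × 50 = 41%, against 35%;
- false OR = (0.41/0.59) / (0.35/0.65) = 1.29, ln OR = 0.255;
- SE = √[3/(65 × 0.35 × 0.65) + 1/(65 × 0.41 × 0.59)] = 0.516;
- bias/SE = 0.255/0.516 = 0.49, so a nominal 5% test rejects 7.8% of the time.

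The false change is 6 points, 6/15 = 40% of the target if the 15% is read as percentage points.

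Fits on expected counts for all cases, 65 per arm per wave:

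| Case (assumed rates) | OR at 30:70 / 70:30 | Largest bias/SE | Largest rejection |
|---|---|---|---|
| (a) as above | 1.29 / 0.76 | 0.52 | 8.2% |
| (a) with shift to 40:60 / 60:40 only | 1.14 / 0.87 | 0.26 | 5.8% |
| (a) rates, one practice of each type per arm | 1.14 / 0.86 | 0.28 | 5.9% |
| (b) same type, intervention 30/40%, control 35/35% | 1.09 / 0.91 | 0.17 | 5.3% |
| (c) one of each type, control 30/35%, intervention 20/60% | 1.16 / 0.85 | 0.30 | 6.0% |
| (d) one of each type, 20/50% in both arms | 1.00 / 1.00 | 0 | 5.0% |

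With practice indicators the OR is 1.00 in every row. Case (a) at 117 or 130 per arm per wave reaches 0.70 or 0.74 SE (rejection 10.8% or 11.5%). With an unchanged mix and no true change, both models give 1.00.

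**With a true effect.** At a true within-practice OR of 2.00 in case (a), the model without practice terms gives 1.86 with no shift. That is non-collapsibility of the odds ratio, not mix bias. The shifts to 30:70 and 70:30 move it to 2.43 and 1.42, factors of 1.31 and 0.76 relative to 1.86. Practice indicators give 2.00 throughout.

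**The case against.** The phrase can fairly be read as saying only that pre-existing differences between intervention and control practices do not drive the result. Protocol section 8 frames the comparison that way, and the model does remove that stable difference. This stands: on that reading the phrase is loose rather than wrong.

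The bias also needs a change in mix that nobody has documented. The protocol's commitment to repeat the baseline procedures argues against a large one, though it does not fix the numbers per practice. Case (a) is extreme: two same-type practices 30 points apart, a 20-point shift in one arm only, and nothing absorbed by the patient covariates. The 40% figure comes from that case alone; in case (b) it is 2/15 = 13%. This stands too and limits the weight of the point.

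The SAP also reports percentages for each arm and wave and tests change within each practice. Those tests could reveal a pure mix shift, but they are unadjusted and do not correct the reported odds ratio.

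A reader might infer two stronger things. The first is that the reported odds ratio is biased; the documents give no counts by practice and wave and so do not support this. The second is that the way arms were chosen causes the problem. Protocol section 2 says the practices are picked at random, while Part I says "The selection of these sites will be determined based on site availability, willingness to participate, and clinic characteristics". That conflict needs resolving, but stable arm differences cancel on the model's scale, so this point does not depend on it.

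**Conclusion.** The stated property is only partly delivered. The shortfall is certain as algebra, given four practices and the usual main effects; six practices would widen it. Its effect on the result is conditional and probably modest. It requires a within-arm mix change between waves together with practice gaps that type and the patient covariates do not capture. At 65 patients per arm per wave it is at most about 0.5 SE in the single-arm illustrations and 0.3 SE or less outside the most extreme one. The same bias counts for more SEs in a larger sample. The practice rates and shifts are assumptions, so the actual size is unknown. The change is worth making because it is cheap; the documents do not show that the result is wrong.

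**What to change.** Fit the regression with practice indicators in place of the arm main effect and practice type, keeping time, arm × time, age, race/ethnicity and reason for visit. Report the number analysed by practice and wave, and confirm that the same four practices supply both waves.

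The SAP is written in the past tense and dated 11/17/2020, so the model may already have been run. If so, report the practice-indicator model as a labelled sensitivity analysis beside the planned one, and narrow the phrase to *adjusting for stable differences between intervention and control practices and for practice type*.

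Cost: a small change to code and wording, with no new data. It uses one extra degree of freedom if type varies within an arm and two if it does not. Under no effect, the interaction SE rises by 0.0–0.6% in case (d), 0.3–1.4% in (b), 1.8–2.7% in (c) and 2.7–3.9% in (a). The largest rise computed is 8.0%, with both arms at 20/50%, same-type practices within each arm and a true OR of 2.00. Practice type no longer has its own coefficient. Clustering, practice-specific time trends and the weak inference from two practices against two all remain.

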### **1. Background**

Effectively delivered preconception counseling leads to healthier pregnancy behaviors (1), and high quality contraceptive counseling leads to more effective birth control use (2-4), both of which improve outcomes for women and their offspring (5-7). The Centers for Disease Control and Prevention (CDC) recommend that primary care and reproductive health providers routinely ask reproductive age patients about their personal goals regarding pregnancy and offer preconception and contraceptive counseling guided by the patient's preferences (8). However, only 14% of ambulatory visits by reproductive age women in the United States include any preconception or contraceptive counseling (9). Many clinicians miss opportunities to provide this counseling because they lack tools to identify women who would benefit from it, and may not have the care processes in place to provide appropriate counseling and access to evidence-based care once the need is identified. This need is addressed through our intervention: the One Key Question® (OKQ), a program run through the nonprofit *Power To Decide* to help clinicians efficiently address women's pregnancy intention and provide evidence-based care (Appendix A). Clinicians are trained to ask patients, "Would you like to become pregnant in the next year?" and address contraception and preconception health in a supportive, patient-centered manner. The program provides clinician and staff training, evidence-based clinical tools, and efficient workflows to implement the CDC recommendations (10, 11). We have collected baseline needs assessment data by surveying patients at 6 obstetrics and gynecology and family medicine groups within Northshore University Health Systems (EH 18-015). All 6 of these clinics (see page 3) have agreed to participate in future trainings and post-intervention survey collection at their sites.

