**7. Type and number of experimental subjects**

Up to 100 clinicians and staff that take part in the OKQ Training. Up to 234 patients from OB and FM clinics will be approached for to be surveyed.

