**12. Procedures to obtain and record informed consent**

- a. While in the waiting room, a researcher will approach a patient who appears to be 18-49, non-pregnant, and female after the patient checks in for her appointment.
- b. The researcher will read the oral recruitment and consent script. The patient has to agree to hear more about the study (after oral recruitment), provide verbal consent, and meet study criteria in order to participate. A one page information sheet (Appendix G) about the study and their rights

as a participant will be given while verbally consenting and if desired patients can take the one pager home to keep. See **Part II: Survey Collection** for more details on the overall recruitment and consenting process.

- c. An information sheet cover letter explaining the study (Appendix F) will be included in both the paper version and electronic version of the survey provided to clinicians and staff. The cover letter will be in the body of the email which contains the link to the survey. The link will be listed after the cover letter. Please see section **Part II: Survey Collection subsection c** for more information.

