### **13. Confidentiality**

No identifying information will be collected during consent or study participation. Participants will be asked to place completed surveys in an opaque envelope before handing over the survey to the RA. At the end of the collection day, the surveys will be stored in a locked unit. All electronic information will be secured on a NorthShore encrypted server.

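### The SAP's 260 patients are not shown to give 80% power for the difference-in-differences, and the protocol caps patients approached at 234

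*SAP*

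**What the plan says.** The sample-size paragraph of the SAP reads: "minimum sample size of 260 was needed to observe a 15% between-group difference in the pre-to-post change in counseling rates with 80% power". On alpha it says only: "The statistical significance level for all tests was <0.05".

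The analysis that this is meant to support is a "multivariable logistic regression with an intervention time point interaction (difference-in-differences) term", fitted to four groups of patients: "baseline time point in control and intervention practices, and post-intervention time point in control and intervention practices".

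The protocol has no power calculation. Its section 7 sets the patient number: "Up to 234 patients from OB and FM clinics will be approached for to be surveyed". Those approached must still "provide verbal consent, and meet study criteria in order to participate" (section 12), and the SAP then excludes patients reporting menopause, hysterectomy or sterilization. Section 13 adds: "No identifying information will be collected during consent or study participation". The only counseling rate in either document is in the protocol's Background: "only 14% of ambulatory visits by reproductive age women in the United States include any preconception or contraceptive counseling".

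**The concern.** The stated target is a difference between two changes, so its variance has four binomial terms. The surveys carry no identifiers, so a patient seen at baseline cannot be linked to one seen after training, and no pairing reduces that variance. With equal cells and the same total, a difference-in-differences has roughly four times the variance of a simple two-group comparison. A figure of 260 looks small for a 15-point effect on that contrast, and the SAP gives none of the inputs needed to check it.

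The power statement tells a reader how to weigh a non-significant interaction. If 80% is wrong, a null result would be read as evidence against a 15-point effect that the design had a much lower chance of detecting. The 260 also exceeds the protocol's 234 if it refers to the post-training wave.

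**Working it through.** **Inputs**

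- From the SAP: N = 260, difference 15% (taken as percentage points), power 80%, alpha 0.05, four groups.
- From the protocol: no patient linkage (section 13); at most 234 approached (section 7). Section 3, Part II covers the post-training survey, and baseline data came from an earlier study.
- Assumed, because not given: 14% in three cells and 29% in the fourth; equal cells; two-sided test; no clustering; no covariates.

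**1. Can 260 be reproduced?**

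Yes, as one comparison of two proportions, 14% vs 29%, with mean 0.215:

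n per group = [1.960 × √(2 × 0.215 × 0.785) + 0.8416 × √(0.14 × 0.86 + 0.29 × 0.71)]² / 0.15² = (1.1387 + 0.4808)² / 0.0225 = 116.6, so 117 per group, or **234** in total.

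With continuity correction: (116.56/4) × [1 + √(1 + 4/(116.56 × 0.15))]² = 129.6, so 130 per group, or **260** in total.

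This calculation returns both documents' numbers. Among whole-percent baselines only 14% and its mirror 71% do so. It suggests that the baseline variance was left out, but does not prove it, since other inputs can also give 260.

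**2. The contrast actually planned**

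Sum of the four binomial variances: 3 × 0.14 × 0.86 + 0.29 × 0.71 = 0.3612 + 0.2059 = 0.5671.

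n per cell for 80% power = (1.960 + 0.8416)² × 0.5671 / 0.15² = 197.8, so 198 per cell, 396 per wave, 792 in total.

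Power = Φ(0.15/SE − 1.960), with SE = √(0.5671/n). On the logit scale the interaction is ln(2.51) = 0.920 and SE = √(29.77/n), where 29.77 = 3/(0.14 × 0.86) + 1/(0.29 × 0.71).

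| Meaning of N | n per cell | SE (risk difference) | Power, risk difference | Power, logit |
|---|---|---|---|---|
| 260 in total | 65 | 0.0934 | 36% | 27% |
| 234 per wave | 117 | 0.0696 | 58% | 45% |
| 260 per wave | 130 | 0.0660 | 62% | 48% |
| 260 per cell | 260 | 0.0467 | 89% | 78% |

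Simulation of 65, 130 and 260 per cell gave 37%, 63% and 89% (risk difference) and 27%, 48% and 78% (logit). A one-sided 0.05 test on the risk-difference scale gives 48% and 73% for the total and per-wave readings. The logit scale needs about 277 per cell for 80%.

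**3. Sensitivity to the assumed 14%**

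| Baseline rate | 260 in total: risk diff. / logit | 260 per wave: risk diff. / logit |
|---|---|---|
| 5% | 59% / 33% | 88% / 57% |
| 7% | 52% / 32% | 81% / 55% |
| 14% | 36% / 27% | 62% / 48% |
| 30% | 25% / 23% | 45% / 41% |
| 50% | 23% / 23% | 41% / 41% |
| 80% | 38% / 51% | 65% / 80% |

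As a total, 260 is below 80% throughout. Per wave, it reaches 80% on the risk-difference scale only at a baseline of about 7% or less, and on the logit scale only from about 80%.

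**4. Could a larger baseline wave rescue it?**

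The variance allowed for 80% power is (0.15/2.8016)² = 0.002867.

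- 130 per arm after training: the post-training part is 0.3263/130 = 0.002510, which leaves 0.000357. Baseline n = 0.2408/0.000357, or about 675 per arm. With 300 per arm at baseline, power is 74%.
- 117 per arm (all 234 analysable): the post-training part is 0.002789, so about 3,100 per arm are needed at baseline. With 300 per arm, power is 71%. On the logit scale power stays at 78% or below for any baseline size.
- 90% of 234 analysable (illustrative, 105.3 per arm): power cannot exceed 77% (logit 74%) for any baseline size.

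**5. The cap**

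Read per cell, 260 needs 2 × 260 = 520 post-training patients; read per wave, it needs 260. Section 7 allows at most 234 to be approached, before refusals and exclusions.

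**The case against.** The arithmetic is not in dispute; the objections concern how much it proves.

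- **What is proved.** The SAP omits its inputs, so strictly the documents show a figure that cannot be checked, not a proven slip. This stands for the cause: the two-group explanation rests on matching two integers.
- **The 14%.** It is a national figure for ambulatory visits, not a planning rate for these clinics, and local baseline data existed. So 36% and 62% are conditional figures to be read with their ranges. This does not rescue the claim, because most mid-range baselines give lower power.
- **The per-cell reading.** It meets 80% at a 14% baseline on the risk-difference scale. It conflicts with the cap, but that is a point about feasibility, not about the calculation.
- **The 234.** It appears to cover the post-training wave only, so it does not contradict 260 as a two-wave total. That is correct, but the total is the reading with the lowest power.
- **Weight.** This is a pilot, and confidence intervals will show the imprecision. The SAP nevertheless makes a specific 80% claim for the efficacy contrast.
- **Clustering and covariates.** Allowing for clustering within four practices would normally lower power further. Covariate adjustment would have to cut the variance by about a third (130/198 = 0.66) or two thirds (65/198 = 0.33) to restore 80%.

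**Conclusion.** The concern holds: 80% power for a 15-point difference-in-differences is not shown. Under the stated assumptions, neither the total nor the per-wave reading of 260 reaches 80% at the only rate the documents offer. The total reading fails at every baseline examined. The per-wave reading succeeds only at the extremes, and at no examined baseline on both scales. The per-cell reading cannot be met within the protocol's cap. Confidence is high that the claim is unsupported as written; that the baseline variance was omitted is a plausible inference only. The point should be fixed, but no test or estimate depends on it.

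**What to change.** 1. State the baseline rate, sidedness, formula and baseline-wave size used, and whether 260 is a total, per wave or per cell.
2. Recompute with the four-group variance on the scale of the planned logistic interaction, say whether clustering by practice is allowed for, and restate the power or the detectable difference. As an illustration only: with 130 per cell, a 14% baseline and no clustering, power for 15 points is about 62%, and about 19 points is detectable at 80%, on the risk-difference scale.
3. If 260 came from a two-group calculation, say so and withdraw the 80% claim for the difference-in-differences.
4. Reconcile 260 with the 234 in protocol section 7, stating which wave each number covers and counting analysable rather than approached patients.

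The cost is wording in the SAP and in protocol section 7. No extra patients are needed and no test or estimate changes. The stated power will probably become less favourable.
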